For oral iron, ferrous sulfate 325 mg tablets containing 65 mg of elemental iron were used. The pills were taken twice daily on an empty stomach. If significant gastrointestinal perturbation occurred the medication could be taken with food. The oral placebo was standard vitamin C 250 mg tablets given in the same bottle as oral iron.

Following the first IV infusion, telephone evaluations were performed at 7, 14 and 28 days. At four weeks after the first of the pair of IV treatment were completed, blood tests were performed to include hemoglobin concentration and iron parameters (serum iron, total iron binding capacity, serum ferritin, percent transferrin saturation). A six weeks after the first of the pair of IV treatment were completed, another clinic visit was scheduled so a CGI form could be completed by involved medical personnel. At 6 weeks, non-responders were given the option of receiving ferumoxytol as an open-label infusion. At the 6-week clinic visit, repeat blood tests (see above), adverse event reporting and clinical evaluation of the RLS was performed.

Inclusion criteria were as follows:

1. Aged \geq 18 years
2. Diagnosis of RLS based on CHDQ and confirmed by HTDI
3. International RLS Study Group Severity Scale (IRLS) score > 15 .
4. Iron deficiency anemia defined as ID either ferritin < 20 mcg/l, TSAT $< 19\%$, anemia Hb < 13 g/dL for both males and females.
5. Willingness to use contraceptive to avoid pregnancy: Women have to be surgically sterile, post menopausal or use one of the following contraceptives during the whole study period and after the study has ended for at least 5 times plasma biological half-life of the investigational medicinal product: intrauterine devices or hormonal contraceptives (contraceptive pills, implants, transdermal patches, hormonal vaginal devices, or injections with prolonged release).
6. Willingness to participate and signing the informed consent form

Exclusion criteria were as follows:

1. Iron overload or disturbances in utilization of iron (e.g. haemochromatosis and hemosiderosis)
2. Decompensated liver cirrhosis or active hepatitis (ALAT > 3 times upper limit of normal)
3. Serum ferritin > 500 ng/mL or transferrin saturation $> 40\%$
4. Active acute or chronic infections (assessed by clinical judgment that may be indicated by white blood cells (WBC) and C-reactive protein (CRP) when these are available)
5. Rheumatoid arthritis with symptoms or signs of active inflammation
6. Pregnant and nursing women

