Subjects could terminate the study at any time for could be terminated from the study for non-compliance or if continuation in the study was judged by the PI ([name]) to be harmful. Reasons for termination were recorded. 21 patients were terminated or lost to follow-up. Some of these terminations may have been due to hiatuses in the study caused by the untimely death of the principal investigator ([name]) and the untimely occurrence of the COVID pandemic, interfering with patient visits. A list of those terminated or lost to follow-up are reported in Table _____. As a result, an additional 30 patients were accrued above the planned prespecified number, to achieve appropriate statistical power.

There were two co-primary outcome measures: Clinician Global Inventory-Improvement (CGI-I) assessment at week 6 and the change-in-baseline at 6 weeks in International RLS Study Group Severity Scale (IRLS) score. The Patient Global Inventory-Severity (PGI-S) was a secondary outcome measure (PGI-S). The IRLS and PGI-S were obtained at the clinic visits and at each telephone evaluation, while the CGI-i was only obtained at the Week-6 study endpoint.

Statistical analysis

Baseline and follow up laboratory values were described overall and within each study group. Means and standard deviations and medians and ranges were produced for continuous variables, and frequency counts and percentages were generated for describing variables that were dichotomous or

polytomous in nature. Changes in laboratory values from baseline to follow up were calculated and the mean change in values was compared using t-tests.

Results

Baseline lab values of all subjects and by Group are found in Table 1. There was a significant difference between baseline ferritin and TSAT values. Group A had a higher baseline ferritin and TSAT values than Group B.

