Change in hemoglobin and iron parameters for all subjects and by group are shown in Table 3. The mean change in hemoglobin from baseline to follow up was 1.2 (SD 1.3) for Group A and 6.0 (17.2) for Group B. The mean change in Ferritin from baseline to follow up was 200.3 and 23.3 for Group A and Group B, respectively. The mean change in TSAT from baseline to follow up was 16.5 and 12.2 for Group A and Group B, respectively. The mean change in MCV from baseline to follow up was 24.2 and -17.6 for Group A and Group B, respectively. There was a significant difference between follow up ferritin and TSAT values. Group A had a higher follow up ferritin values ($p=0. <0.0001$) and higher TSAT ($p=0.007$) values compared to Group B.

Table 4 shows the changes in patient severity scores from baseline to follow up, and the follow up patient and clinical global impression scores for all subjects and by group. No significant differences between the 2 groups in terms of change in (1) patient severity score from baseline to follow up, (2) follow up patient global impression score, or (3) clinical global impression score were observed.

Table 5 shows the change in FSS from baseline to follow up. There were no significant differences between the 2 groups in terms of change in FSS.

Table 6 shows the change in IRLS score from baseline to follow up for all subjects and by group. Group B had a greater reduction in IRLS score from baseline to follow up compared to Group A

NOT SURE IF/HOW YOU WANT TO PRESENT THE ADVERSE REACTION DATA

Commented [VS1]: These are results from my original analysis. I still need to double check the results. However, before doing so, I want to confirm that there are no new data to analyze.

Commented [VS2]: Will define "Group A" and "Group B" once I know which group is which

TABLES**Table 1. Baseline hemoglobin and iron parameters for all subjects and by group.**

	Total	Group A	Group B	P-value¹
Hemoglobin	N=93	N=47	N=46	0.14
Mean (SD)	11.1 (1.5)	11.3 (1.3)	10.8 (1.6)	
Median (IQR)	11.6 (10.2, 12.2)	11.7 (10.8, 12.3)	11.6 (9.7, 12.1)	
Min, Max	7.0, 13.1	7.2, 13.1	7.0, 13.0	
Ferritin	N=91	N=45	N=46	0.017
Mean (SD)	17.9 (16.7)	22.6 (19.6)	13.5 (12.1)	
Median (IQR)	11.0 (7, 24)	19 (7, 29)	10.0 (7-15)	
Min-Max	3, 102	4, 102	3.0, 59.0	
TSAT	N=92	N=46	N=46	0.025
Mean (SD)	10.4 (6.2)	11.4 (5.9)	9.5 (6.5)	
Median (IQR)	9.0 (6, 13)	10.0 (8, 15)	8.5 (6.0-11.0)	
Min-Max	2, 36	2, 36	2, 32	
MCV	N=93	N=47	N=46	0.233

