Mean (SD)	88.7 (77.3)	82.2 (7.8)	95.4 (110.4)	
Median (IQR)	83 (75.5, 87.0)	83.9 (77.9, 86.3)	81.5 (71.6-87.0)	
Min-Max	56.5, 825.0	58.7, 100.0	56.5, 825.0	

¹ P value comparing Group A vs. Group B using Kruskal-Wallis Test.

Table 2. Follow-up hemoglobin and iron parameters for all subjects and by group.

	Total	Group A	Group B	P-value¹
Hemoglobin	n=70	N=36	N=33	.833
Mean (SD)	14.4 (11.8)	12.5 (1.0)	16.6 (17.0)	
Median (IQR)	12.4 (11.7, 13.3)	12.6 (11.9, 13.2)	12.3 (11.7, 13.4)	
Min-Max	9.7, 105.0	10.4, 14.3	9.7, 105.0	
Ferritin	n=70	N=36	N=33	<0.0001
Mean (SD)	132.8 (136.7)	223.4 (136.6)	37.1 (29.5)	
Median (IQR)	66.5 (27.0, 214.0)	209.5 (127.5, 308.5)	33.0 (21.0-40.0)	
Min-Max	7.0, 620.0	11.0, 620.0	7.0, 159.0	
TSAT	n=70	N=36	N=33	0.026
Mean (SD)	24.4 (13.3)	27.7 (10.0)	21.4 (15.5)	
Median (IQR)	24.0 (14.0, 31.0)	28.0 (20.5, 32.0)	16.0 (12.0-28.0)	
Min-Max	7.0, 89.0	13.0, 59.0	7.0, 89.0	
MCV	n=70	N=36	N=33	0.21
Mean (SD)	95.1 (93.7)	106.4 (130.2)	83.3 (10.6)	
Median (IQR)	86.0 (82.0-88.6)	86.8 (82.7, 88.8)	85.1 (80.0-88.1)	
Min-Max	36.8, 864.0	36.8, 864.0	38.7, 101.0	

¹ P value comparing Group A vs. Group B using Kruskal-Wallis Test.

Table 3. Change in hemoglobin and iron parameters from baseline to follow up for all subjects and by group.

	Total	Group A	Group B	P-value¹
Hemoglobin	N=70	N=36	N=33	0.17
Mean (SD)	3.5 (12.0)	1.2 (1.3)	6.0 (17.2)	
Median (IQR)	1.4 (0.2-2.3)	1.4 (0.2, 1.8)	1.7 (0.3, 3.3)	
Min-Max	-0.9, 95.6	-0.9, 5.0	-0.9, 95.6	
Ferritin	N=67	N=34	N=33	<0.0001
Mean (SD)	113.1 (130.4)	200.3 (133.0)	23.3 (21.2)	
Median (IQR)	35.0 (18, 579)	190.0 (103.0, 290.0)	20.0 (9.0, 27.0)	
Min-Max	-7, 579	-1.0, 579.0	-7.0, 102.0	
TSAT	N=68	N=35	N=33	0.007
Mean (SD)	14.4 (12.6)	16.5 (7.5)	12.2 (16.3)	
Median (IQR)	13.5 (6.5, 19.4)	16.0 (11.0, 20.0)	7.0 (3.0, 18.0)	
Min-Max	-17.0, 82.0	-5.0, 37.7	-17.0, 82.0	
MCV	N=70	N=36	N=33	0.49
Mean (SD)	4.2 (129.9)	24.2 (130.9)	-17.6 (129.5)	
Median (IQR)	3.2 (-0.2, 8.2)	3.3 (-0.4, 7.6)	3.1 (1.2, 9.5)	
Min-Max	-736.9, 784.4	-58.4, 784.4	-736.9, 21.1	

¹ P value comparing Group A vs. Group B using Kruskal-Wallis Test.

Table 4. Change in patient severity scores from baseline to follow up, and follow up patient and clinical global impression scores for all subjects and by group.

	Total	Group A	Group B	P-value¹
Change in patient severity score²	N=57	N=30	N=27	0.24
Mean (SD)	-1.9 (1.8)	-1.7 (1.8)	-2.1 (1.9)	
Median (IQR)	-2.0 (-3.0, -1.0)	-2.0 (-3.0, -1.0)	-3.0 (-4.0, -1.0)	
Min-Max	-5.0, 2.0	-5.0, 2.0	-5.0, 2.0	

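### Implausible hemoglobin and MCV values distort three mean changes in the SAP Results; the stated test is not the one tabulated, one TSAT p-value is misplaced, and several totals do not match their arms

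*SAP*

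**What the plan says.** The SAP section on statistical analysis promises full summaries ("Means and standard deviations and medians and ranges were produced for continuous variables") and names a test for laboratory changes: "Changes in laboratory values from baseline to follow up were calculated and the mean change in values was compared using t-tests". The footnote to Table 3, which holds those changes, reads "P value comparing Group A vs. Group B using Kruskal-Wallis Test". Tables 1 and 2 carry the same footnote.

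The Results then give mean changes without medians. For hemoglobin: "The mean change in hemoglobin from baseline to follow up was 1.2 (SD 1.3) for Group A and 6.0 (17.2) for Group B". For MCV: "The mean change in MCV from baseline to follow up was 24.2 and -17.6 for Group A and Group B, respectively". For TSAT at follow-up, Group A is said to have "higher TSAT ($p=0.007$) values compared to Group B".

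The SAP fixes the hemoglobin unit in its inclusion criteria: "anemia Hb < 13 g/dL for both males and females". Table 2 nevertheless prints a Group B follow-up maximum of 105.0. Table 1 prints a Group B baseline MCV maximum of 825.0, and Table 2 a Group A follow-up MCV maximum of 864.0.

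**The concern.** A reader of the Results text alone learns that hemoglobin rose five times as much in Group B as in Group A, and that MCV rose in one group and fell in the other. The medians in Table 3 show something else: hemoglobin +1.4 (A) and +1.7 (B), MCV +3.3 (A) and +3.1 (B). The contrast in MCV direction and the size of the hemoglobin contrast come from a handful of records that look like data errors.

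Three reporting faults sit beside this. The named test is not the one used. A p-value for change is attached to follow-up values. Several totals do not agree with the arms they should sum. At stake is whether the laboratory results can be relied on as printed. Because one count fault is in the IRLS table, it also matters whether the number analysed for a co-primary outcome is known.

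**Working it through.** **Inputs.** SAP Tables 1, 2, 3 and 6, as printed. Each extreme change is assumed to belong to the record with the extreme value.

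**1. Reproducing the printed figure.** Hemoglobin change from the arms: (36 × 1.2 + 33 × 6.0)/69 = 3.50, against 3.5 printed. The text and Table 3 agree.

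**2. Tracing the extremes.** Each gives an otherwise ordinary record:
- Hemoglobin: 105.0 − 95.6 = 9.4 at baseline
- MCV, Group B: 825.0 − 736.9 = 88.1 at follow-up
- MCV, Group A: 864.0 − 784.4 = 79.6 at baseline

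**3. Leaving out one value.** New mean = (n × mean − x)/(n − 1). The SD is adjusted through the sum of squares.

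| Change | Printed mean (SD) | Calculation | Without it |
|---|---|---|---|
| Hemoglobin, B | 6.0 (17.2) | (33 × 6.0 − 95.6)/32 | 3.2 (6.2) |
| MCV, A | 24.2 (130.9) | (36 × 24.2 − 784.4)/35 | 2.5 (12.5) |
| MCV, B | −17.6 (129.5) | (33 × (−17.6) + 736.9)/32 | +4.9 (10.0) |

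These means are still not clean. Group A also has an MCV change of −58.4. Leaving that out too gives (871.2 − 784.4 + 58.4)/34 = 4.3 (SD about 6.7). In Group B, follow-up hemoglobin without 105.0 is (33 × 16.6 − 105.0)/32 = 13.8, with SD still 6.2. If the other 31 values have an SD of 1 to 2 (assumption), that implies one further value near 46 to 47.

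**4. The stated test on the printed summaries of change (Table 3).**

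| Variable | Welch p | Pooled p | Table 3 (Kruskal-Wallis) |
|---|---|---|---|
| Hemoglobin | 0.12 | 0.10 | 0.17 |
| TSAT | 0.17 | 0.16 | 0.007 |
| MCV | 0.19 | 0.19 | 0.49 |
| Ferritin | <0.0001 | <0.0001 | <0.0001 |

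For TSAT change, Welch t = (16.5 − 12.2)/√(7.5²/35 + 16.3²/33) = 4.3/3.11 = 1.38. Without the single +82 change, Group B becomes 10.0 (SD 10.6, n = 32) and Welch p is about 0.006.

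**5. Do the named values decide significance?** After their removal, Welch p is 0.08 for hemoglobin, and 0.39 for MCV (about 0.77 if −58.4 also goes). By normal approximation the rank p goes from 0.17 to about 0.24 for hemoglobin if B ranks higher. For MCV it goes from 0.49 to 0.25 or 0.77, depending on a direction that is not printed. None crosses 0.05.

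**6. TSAT p-values.** Table 2 (follow-up values): 0.026. Table 3 (change): 0.007. The Results attach 0.007 to follow-up values.

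**7. Totals.**
- All rows of Table 2, and hemoglobin and MCV in Table 3, print 70, but 36 + 33 = 69.
- Table 2 ferritin: (36 × 223.4 + 33 × 37.1)/69 = 134.3, against 132.8 printed.
- Table 2 TSAT: (36 × 27.7 + 33 × 21.4)/69 = 24.7, against 24.4 printed.
- Table 3 ferritin total (N = 67): the upper quartile is printed as 579, which is the maximum. Group B has no value above 102, and Group A (n = 34) has a median of 190. The 17th value from the top is therefore about 190.
- Table 6 (IRLS): 37 + 36 = 73 against 74, and the footnoted follow-up counts give 2 + 4 + 5 + 61 = 72.

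**The case against.** The strongest reply is that this is proofreading of draft laboratory results. The analyst's margin note says the results still need checking. Medians and ranges stand beside every mean in the tables. Kruskal-Wallis uses ranks and hardly feels the outliers. The text claims no hemoglobin or MCV difference, and MCV is not even among the tests listed where "blood tests were performed to include hemoglobin concentration and iron parameters". All of this is true and limits the weight of the point. It does not correct the means in the text, and the note names none of these faults.

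Four stronger readings are tempting, and the documents do not support them.
- **A reader might infer that Kruskal-Wallis was adopted after the t-test results were seen.** Nothing says when or why it was chosen. The protocol names a t-test only for IRLS change and sets none for laboratory changes. The sentence in the SAP may itself be the error.
- **A reader might infer that one patient was counted in neither arm.** The misfit of the Table 2 means is compatible with that. However, the Table 3 totals for ferritin (34 + 33 = 67) and TSAT (35 + 33 = 68) equal their arm sums, which a simple unassigned record does not explain. A duplicate or another error is equally open.
- **A reader might infer that the larger hemoglobin rise in Group B is spurious.** Only its size is shown to be distorted; the medians point the same way.
- **A reader might take the choice of test to overturn a stated TSAT conclusion.** The significance sentence concerns follow-up values, and both printed TSAT p-values are below 0.05.

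The opposite reassurance, that nothing here touches the co-primary outcomes, is also too broad. It holds for the laboratory outliers but not for the counts in Table 6.

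**Conclusion.** The point holds, as a should-fix matter. Three reported mean changes are distorted by single values: by about 2.8 for hemoglobin in Group B (6.0 − 3.2), 21.7 for MCV in Group A (24.2 − 2.5), and 22.5 with a change of sign for MCV in Group B (−17.6 to +4.9). The replacement figures are illustrative, because further suspect values remain and source has not been seen.

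The stated and tabulated tests differ, and for TSAT change they disagree across 0.05. One TSAT p-value is misattributed. The counts in Tables 2, 3 and 6 do not reconcile, for reasons the documents do not establish, and the total ferritin quartile of 579 cannot be right.

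Removing the named hemoglobin and MCV values moves no hemoglobin or MCV p-value across 0.05. That statement does not extend to any further hemoglobin outlier still in Group B.

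**What to change.** - **Query against source and log each outcome:** hemoglobin 105.0 and any further Group B hemoglobin outlier; MCV 825.0, 864.0, 36.8 and 38.7; and the record with the −58.4 MCV change. Correct to source. Set to missing only values that are impossible and cannot be verified, and show results with and without them.
- **Check TSAT 89 and the +82 change,** but keep them unless source shows an error, since dropping that one change moves the t-test from about 0.17 to about 0.006.
- **Reconcile the counts and totals** in Tables 2, 3 and 6, correct the total ferritin quartile, and rerun the tables.
- **In the Results,** give medians (IQR) beside the mean laboratory changes. Give follow-up TSAT its Table 2 p-value and TSAT change its Table 3 p-value, both from the rerun.
- **Reconcile the statistical analysis section with the table footnotes.** For laboratory changes, report the stated t-test on corrected data beside Kruskal-Wallis. Say which is the main test, and when and why Kruskal-Wallis was adopted.

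The cost is a few record queries, one rerun and a few rewritten sentences. The downside is two p-values per laboratory change, which may disagree for TSAT.
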